1.1 Study Objective (s)

1.1.1 Primary objective (s)

The primary objective of this study is to determine the safety of CD5789 50 µg/g cream in the long-term treatment (up to 52 Weeks) of subjects with acne vulgaris.

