3.2.3 Laboratory safety tests

The laboratory analyses will be based on Central laboratory results. The following laboratory safety tests will be performed at the Screening visit, Week 26 and Week 52/ET visits. Abnormal laboratory results will be evaluated by the investigator as clinically significant or non-clinically significant.

- Hematology: White blood cell (WBC) count with differential, red blood cell (RBC) count, hemoglobin(Hb), hematocrit (Hct), mean cell volume (MCV), and platelet count (Plt)
- Blood chemistry: Creatinine, uric acid, urea nitrogen, gamma glutamyl transferase (GGT or γ GTP), alkaline phosphatase (ALP), aspartate aminotransferase (ASAT=SGOT [AST in US]), alanine aminotransferase (ALAT=SGPT [ALT in US]), and bilirubin (total, direct & indirect).
- Urinalysis: blood, proteins, leukocytes, glucose

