7.6 Vital Signs and Physical Exam

The descriptive statistics for Vital Signs collected at each visit and changes from Baseline will be provided. Nominal eCRF visit will be used as analysis visit.

Physical exam will be provided in a subject-by-subject listing.

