7.9 Analysis visit definition

For efficacy, DLQI/ C-DLQI and local tolerability data, analysis visit will be assigned according to the algorithm in Table 3 below to summarize the data by proper visit window interval. Study day is calculated as visit date minus the date of first application plus 1. If multiple measurements are taken in the same interval, the one closest to the target study day will be used for the analysis. If two measurements are taken with equal differences in timing compared with the target date, the nominal visit number (recorded on the CRF page) will be used. If there is missing measurement at Baseline, Screening data will be used to impute the missing baseline data, i.e. Baseline will be the last available data prior to first application of study drug.

Table 3 Analysis Visit and Visit Window

Analysis Visit	Analysis Visit Number in Derived Dataset	Target Study Day	Visit Window (Study Day)
Baseline	1	1	[≤1]
Week 1	2	8	[2 – 11]
Week 2	3	15	[12 – 21]
Week 4	4	29	[22 – 42]
Week 8	5	57	[43 – 70]
Week 12	6	85	[71 – 112]
Week 20	7	141	[113 – 161]
Week 26	8	183	[162 – 224]
Week 38	9	267	[225 – 315]
Week 52	10	365	> 315

When assigning the analysis visits for vital signs, no visit window will be applied; Nominal eCRF visit will be used as analysis visit for summaries. Only data from schedule visit will be summarized.

When assigning the analysis visits for laboratory data, no visit window will be applied, however, the following rules will be applied:

1. If sample date is at or prior to date of first application, the data will be considered as screening visit. If multiple measurements of screening due to rescreening, retest or other unexpected reasons, the data closest to date of first application will be chosen.
2. Lab data from scheduled visit will be considered first when assigning analysis visit of each scheduled visit. If there is no data from scheduled visit available, the last of those corresponding unscheduled visit will be considered for assignment of analysis visits.
3. When assigning Final visit, the lab data from the last post-baseline scheduled visit during treatment period will be considered first. If the last scheduled visit during treatment period have missing lab data due to any reason and there are subsequent unscheduled lab data available, the last of those corresponding unscheduled lab data will be assigned as Final visit. Otherwise, the previous visit lab data will be considered in the same manner.

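### Laboratory and vital-sign data have no visit window, so unless the eCRF separates them, early-termination values share the last by-visit row with one-year values

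*SAP*

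**What the plan says.** SAP section 7 sends laboratory tests and vital signs, like the efficacy variables, to section 7.9 for their analysis visit. Section 7.9 then treats the data types differently.

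- **Efficacy, DLQI/C-DLQI and local tolerability** are placed by study day in the windows of Table 3. Only values after Study Day 315 count as Week 52.
- **Laboratory data:** "When assigning the analysis visits for laboratory data, no visit window will be applied". Rule 2 adds "Lab data from scheduled visit will be considered first when assigning analysis visit of each scheduled visit", with unscheduled results as a fallback. Rule 3 defines a separate Final visit.
- **Vital signs:** "Nominal eCRF visit will be used as analysis visit for summaries", followed by "Only data from schedule visit will be summarized". Section 7.6 repeats the nominal-visit rule. No Final visit is defined for vital signs.

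On the schedule, section 3.2.3 states that laboratory tests "will be performed at the Screening visit, Week 26 and Week 52/ET visits". Section 3.2.4 puts vital signs at Screening, Baseline, Weeks 12 and 26, and a last visit that again joins Week 52 with ET. Sections 7.5.4 and 7.6 summarise values and changes from baseline at each visit.

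**The concern.** The primary objective (section 1.1.1) is long-term safety up to 52 weeks. Laboratory parameters and vital signs are two of the four safety endpoints in section 4.2. The study is open-label, non-comparative and purely descriptive, so the by-visit change from baseline is the summary in which a gradual shift over a year would show.

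If the last row mixes subjects treated for a year with subjects who left after a few weeks, its mean no longer describes one year of exposure. Should early leavers show less change, the row understates the change at one year. Laboratory tests have only two post-baseline visits. For anyone leaving before Week 26, the ET sample is therefore the only scheduled post-baseline result, and it falls in that row.

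**Working it through.** The SAP states no dropout rate and no figure for this row, so there is nothing of its own to reproduce. The check has two parts: what the rules do, and how large the effect could be.

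**1. The rules, applied to one subject.** Take an ET visit on Study Day 42.
- Tolerability score: Table 3 places Days 22–42 in Week 4.
- Laboratory value: no window; the scheduled visit is Week 52/ET, so it enters the last row.
- Vital signs, if Week 52/ET is one nominal visit: last row.
- Vital signs, if ET is not regarded as scheduled: left out of the summary. The Week 52 row is then clean. A subject leaving before Week 12 contributes no post-baseline vital signs, while a later leaver keeps the Week 12 and, where reached, Week 26 values.

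No sentence in the SAP chooses between the two vital-sign readings.

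**2. Share of ET values in a pooled row.** Inputs: N = 450 (section 6); d = dropout before Week 52 (assumed); a = proportion of early leavers with an ET value (assumed).

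Share = N·d·a / [N·(1 − d) + N·d·a]

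| d | a = 1.0 | a = 0.7 |
|---|---|---|
| 10% | 45/450 = 10% | 31.5/436.5 = 7% |
| 20% | 90/450 = 20% | 63/423 = 15% |
| 30% | 135/450 = 30% | 94.5/409.5 = 23% |
| 40% | 180/450 = 40% | 126/396 = 32% |
| 50% | 225/450 = 50% | 157.5/382.5 = 41% |
| 77.8% (100 of 450 reach one year) | 350/450 = 78% | 245/345 = 71% |

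The last line uses the one-year exposure floor in section 6. It is a limit, not a forecast.

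**3. Dilution of the mean change.** Section 6 also sets a floor of 300 subjects at 6 months. At both floors, 100 subjects reach one year, 300 − 100 = 200 leave between 6 months and one year, and 450 − 300 = 150 leave earlier. Suppose drift is linear, reaching D at one year, and every leaver is measured. The 200 then show at least 0.5D and the 150 at least 0:

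Row mean ≥ (100 × 1 + 200 × 0.5 + 150 × 0)/450 × D = 200/450 × D = 0.44D

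Dilution is therefore at most 1 − 0.44 = 0.56, about 56%. The bound needs ET attendance not to be selective. In the extreme case where only the 150 earliest leavers were measured, the mean would be 100/250 = 0.40D.

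**4. Effect of a Day 315 limit.** If departures were spread evenly over Days 2–364 (assumed), (364 − 315)/(364 − 1) = 49/363 = 13% of ET values would still qualify as Week 52 and about 87% would move out of that row.

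**The case against.** The strongest reply is that Week 52/ET is schedule wording. The SAP uses the same label for IGA, PGA, self-assessment and DLQI, which are then placed by study day, so the label alone does not prove pooling. The eCRF is not shown and may hold ET as its own visit. A pooled row might also be headed Week 52/ET. All of this stands. A reader might infer that the SAP definitely reports early leavers' values as 52-week data, but the text does not go that far. Even so, an honest row label would still mix unlike exposures, and the SAP leaves the matter open.

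A reader might also infer that the row is wrong under either reading of ET. It is not: if ET is not a scheduled visit, the vital-sign Week 52 row is clean, and the cost is the omitted ET values. Nor would all vital signs of early leavers be lost.

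The laboratory plan has safeguards. Rule 3's Final visit, the shift table to the last post-baseline visit, and the listings of out-of-range and clinically significant results are unaffected, so individual signals do not hang on this row. They do not supply a one-year by-visit summary, however. If ET is pooled, the last row comes close to repeating Final.

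Nominal assignment for sparsely scheduled assessments is a defensible choice, and departing from Table 3 is not in itself an error. The gap is that ET has no stated place.

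**Conclusion.** The point holds in a limited form. On the plain reading of sections 3.2.3, 3.2.4 and 7.9, early-termination laboratory and vital-sign values fall in the same by-visit row as values after one year, and no other by-visit summary isolates one-year exposure. This is conditional on the eCRF not separating ET. For laboratory data, nominal assignment is inferred from the absence of a window together with rule 2; it is stated outright only for vital signs.

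The size depends on dropout and ET attendance, neither of which the SAP gives. A pooled row would hold 10% to 50% early leavers at 10% to 50% dropout if all are measured, and 7% to 41% if 70% are. The 78% is only an upper bound at the one-year exposure floor. It should not be read as the expected share or as the dilution of the mean change: with linear drift, both floors met and every leaver measured, that dilution is at most about 56%.

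The change is worth making before the tables are programmed, because as written two programmers could produce different Week 52 rows.

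**What to change.** In section 7.9:

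1. For laboratory and vital-sign summaries, limit the Week 52 row to values after Study Day 315, the limit already in Table 3.
2. Show earlier ET values in a separate Early termination row for both data types. This is tidier than applying all of Table 3, because several of its windows (Week 4 and Week 38, for example) have no scheduled laboratory or vital-sign visit.
3. Keep ET laboratory values in the existing Final visit. Leave the scheduled-before-unscheduled rules otherwise unchanged.
4. State that ET vital signs are included despite the sentence restricting summaries to scheduled visits. Vital signs have no Final visit, so the Early termination row is where they would appear.

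The cost is a few lines of SAP text, one extra row per table and a smaller N in the Week 52 row. No new data are needed.

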8 CHANGES FROM THE PROTOCOL ANALYSIS PLAN

There are no changes from the planned analyses on Protocol.

9 TABLE SHELLS AND REPORTING OUTPUT (GENERAL FEATURES)

The tentative list of tables to be produced in the reporting of this study is shown below. All eCRF data will also be available as subject listings and the eCRF data will be available in CDISC compliant data set.

Demographic and Baseline Characteristics tables

- Summary of Subject Enrollment
- Summary of Subject Enrollment by Analysis Center/Site, SAF Population
- Summary of Subject Disposition, SAF Population
- Summary of Subject Disposition by Analysis Center/Site, SAF Population
- Summary of Subject Disposition by Study Duration, SAF Population
- Listing of Discontinued Subjects, SAF Population
- Summary of Subject Demographics and Baseline Characteristics, SAF Population
- ATC Class, WHO Drug and Drug Name, SAF Population
- Summary of Previous Therapy, SAF Population
- Summary of Concomitant Therapy, SAF Population
- System Organ Class, Preferred Term and Procedure/Non-drug Therapy, SAF Populations
- Summary of Previous Procedure / Non-Drug Therapy, SAF Population
- Summary of Concomitant Procedure/Non-drug Therapy, SAF Population

Efficacy tables

- Summary of Success Rate of Investigator's Global Assessment, SAF Population
- Summary of Success Rate of Physician Global Assessment, SAF Population
- Summary of Investigator's Global Assessment, SAF Population
- Summary of Physician Global Assessment, SAF Population
- Summary of Subject Self-Assessment of Acne, SAF Population
- Summary of Dermatology Life Quality Index (DLQI) Total Score, SAF Population
- Summary of Children Dermatology Life Quality Index (CDLQI) Total Score, SAF Population
- Summary of Dermatology Life Quality Index (Adult and Child) Total Score, SAF Population
- Summary of Dermatology Life Quality Index (DLQI) by Dimension, SAF Population

- Summary of Children Dermatology Life Quality Index (CDLQI), SAF Population
- Summary of Success Rate of Investigator's Global Assessment by Gender, SAF Population
- Summary of Success Rate of Investigator's Global Assessment by Race, SAF Population
- Summary of Success Rate of Investigator's Global Assessment by Age, SAF Population
- Summary of Success Rate of Investigator's Global Assessment by Country, SAF Population
- Summary of Success Rate of Investigator's Global Assessment by Skin Phototype, SAF Population
- Summary of Success Rate of Physician Global Assessment by Gender, SAF Population
- Summary of Success Rate of Physician Global Assessment by Race, SAF Population
- Summary of Success Rate of Physician Global Assessment by Age, SAF Population
- Summary of Success Rate of Physician Global Assessment by Country, SAF Population
- Summary of Success Rate of Physician Global Assessment by Skin Phototype, SAF Population

Safety tables

- Summary of Study duration, SAF Population
- Summary of Treatment duration, SAF Population
- Summary of Study Medication Usage and Compliance, SAF Population
- System Organ Class (SOC), Preferred Term (PT) and AE Diagnosis, SAF Population
- Summary of Overall Adverse Events, SAF Population
- Summary of Adverse Events by System Organ Class and Preferred Term, SAF Population
- Summary of Adverse Events by Preferred Term, SAF Population
- Summary of Serious Adverse Events by System Organ Class and Preferred Term, SAF Population
- Listing of Serious Adverse Events, SAF Population
- Summary of Adverse Events Leading to Discontinuation by System Organ Class and Preferred Term, SAF Population
- Listing of Adverse Events Leading to Discontinuation, SAF Population
- Summary of Adverse Events Related to Study Drug by System Organ Class and Preferred Term, SAF Population
- Summary of Adverse Events Related to Study Drug by Preferred Term, SAF Population
- Listing of Adverse Events Related to Study Drug, SAF Population

- Summary of Severe Adverse Events by System Organ Class and Preferred Term, SAF Population
- Listing of Severe Adverse Events, SAF Population
- Summary of Adverse Events of Special Interest by System Organ Class and Preferred Term, SAF Population
- Listing of Adverse Events of Special Interest, SAF Population
- Listing of Subjects with Positive Urine Pregnancy Test Results, SAF Population
- Summary of Vital Signs and Physical Examinations, SAF Population
- Summary of Overall Adverse Events by Gender, SAF Population
- Summary of Overall Adverse Events by Race, SAF Population
- Summary of Overall Adverse Events by Age, SAF Population
- Summary of Overall Adverse Events by Country, SAF Population
- Summary of Overall Adverse Events by Skin Phototype, SAF Population
- Summary of Adverse Events by System Organ Class and Preferred Term by Gender, SAF Population
- Summary of Adverse Events by System Organ Class and Preferred Term by Race, SAF Population
- Summary of Adverse Events by System Organ Class and Preferred Term by Age, SAF Population
- Summary of Adverse Events by System Organ Class and Preferred Term by Country, SAF Population
- Summary of Adverse Events by System Organ Class and Preferred Term by Skin Phototype, SAF Population
- Summary of chronology of Adverse Events, SAF Population
- Summary of Erythema on the Face, SAF Population
- Summary of Scaling on the Face, SAF Population
- Summary of Dryness on the Face, SAF Population
- Summary of Stinging/Burning on the Face, SAF Population
- Summary of Erythema on the Trunk, SAFT Population
- Summary of Scaling on the Trunk, SAFT Population
- Summary of Dryness on the Trunk, SAFT Population
- Summary of Stinging/Burning on the Trunk, SAFT Population
- Summary of Erythema Worse than Baseline on the Face, SAF Population

- Summary of Scaling Worse than Baseline on the Face, SAF Population
- Summary of Dryness Worse than Baseline on the Face, SAF Population
- Summary of Stinging/Burning Worse than Baseline on the Face, SAF Population
- Summary of Erythema Worse than Baseline on the Trunk, SAFT Population
- Summary of Scaling Worse than Baseline on the Trunk, SAFT Population
- Summary of Dryness Worse than Baseline on the Trunk, SAFT Population
- Summary of Stinging/Burning Worse than Baseline on the Trunk, SAFT Population
- Summary of Erythema Worse than Baseline on the Face by Gender, SAF Population
- Summary of Scaling Worse than Baseline on the Face by Race, SAF Population
- Summary of Dryness Worse than Baseline on the Face by Age, SAF Population
- Summary of Stinging/Burning Worse than Baseline on the Face by Country, SAF Population
- Summary of Erythema Worse than Baseline on the Trunk by Gender, SAFT Population
- Summary of Scaling Worse than Baseline on the Trunk by Race, SAFT Population
- Summary of Dryness Worse than Baseline on the Trunk by Age, SAFT Population
- Summary of Stinging/Burning Worse than Baseline on the Trunk by Country, SAFT Population
- Listing of Central Laboratory Data Normal Ranges
- Summary of Laboratory Data - Hematology, SAF Population
- Summary of Laboratory Data - Blood Chemistry, SAF Population
- Summary of Laboratory Data - Urine Drug Screen, SAF Population
- Shift table of Laboratory Data from Baseline to last visit - Hematology, SAF Population
- Shift table of Laboratory Data from Baseline to last visit - Blood Chemistry, SAF Population
- Shift table of Laboratory Data from Baseline to last visit - Urine Drug Screen, SAF Population
- Listing of subjects with Laboratory Data Out of Reference Range, SAF Population
- Listing of subjects with Clinical Significant Laboratory Data, SAF Population
- Listing of subjects with Positive Urine Pregnancy Test Results, SAF Population

Pharmacokinetic tables

- Listing of Individual Subject Plasma Concentration and Pharmacokinetic Parameters, SAF Population PK evaluable subjects
- Summary of Plasma Concentration and Pharmacokinetic Parameters (with imputation and without imputation), SAF Population PK evaluable subjects

Figures

- Success Rate of Investigator's Global Assessment, SAF Population
- Success Rate of Physician Global Assessment, SAF Population
- Erythema Worse than Baseline on the Face, SAF Population
- Scaling Worse than Baseline on the Face, SAF Population
- Dryness Worse than Baseline on the Face, SAF Population
- Stinging/Burning Worse than Baseline on the Face, SAF Population
- Erythema Worse than Baseline on the Trunk, SAFT Population
- Scaling Worse than Baseline on the Trunk, SAFT Population
- Dryness Worse than Baseline on the Trunk, SAFT Population
- Stinging/Burning Worse than Baseline on the Trunk, SAFT Population

Subject data listings

- Prematurely Discontinued Subjects
- Completed Subjects
- Screen Failed Subjects
- Subject Randomization
- Demographics and Baseline Characteristics
- Inclusion/Exclusion Criteria Not Met
- Medical History
- Therapy
- Procedure/Non-Drug Therapy
- General Comments
- Study Medication Compliance
- Study Medication Usage
- Investigator's Global Assessment, Physician Global Assessment, Lesion Counts and Subject Self-Assessment of Acne

- Success of Investigator's Global Assessment and Physician Global Assessment (Derived Efficacy Variables)
- Children's Dermatology Life Quality Index Score
- Local Tolerability Assessment
- Adverse Events
- Adverse Event Comments
- Vital Signs
- Physical Examinations
- Pregnancy Test
